8. Applied SOPs.....	14

1. Objective of PMS

To analyze safety and efficacy information on Pergoveris™ in post-marketing uses, as well as factors likely to influence safety and efficacy

Primary objective: To get safety information in subjects using Pergoveris™

- 1) Serious Adverse Event (SAE)
 - ① If causing death or threatening one's life
 - ② If hospitalization or prolonged duration of hospitalization is necessary
 - ③ If causing continuous or significant disability or dysfunction
 - ④ If causing congenital malformation or abnormality
 - ⑤ Other medically critical conditions
- 2) Adverse event/adverse drug reaction unexpected in precautions
- 3) Already known adverse drug reaction
- 4) Non-serious adverse drug reaction
- 5) Other safety/efficacy related information (influence upon clinical laboratory value, etc.)

2. Patient population

Women with serious deficiency of Luteinizing Hormone (LH) and Follicle-Stimulating Hormone (FSH) at less than 1.2 IU/L of endogenous serum LH

3. Sample size

A total of 600 cases or more shall be reported as per the number of report cases pursuant to the Paragraph 3 of Article 6 of the 'Re-examination Standards for New Drugs Etc.' (Ministry of Food and Drug Safety Notification No. 2014-61).

4. Study items

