5.5 Pergoveris™ exposure

Pergoveris™ exposure will be analyzed as below.

- **Administration period**

Administration period is defined as the sum of each administration period and will be summarized as descriptive statistics. Also, the administration period will be classified as two levels (\leq median, $>$ median) and presented by the frequency and percentage for each level.

- **Total dose**

Total dose is defined as the sum of total doses on each administration period and will be summarized as descriptive statistics. Also, the total dose will be classified as two levels (\leq median, $>$ median) and presented by the frequency and percentage for each level.

- **Average daily dose**

Average daily dose is defined as total dose divided by administration period and will be summarized as descriptive statistics. Also, the average daily dose will be classified as two levels (\leq median, $>$ median) and presented by the frequency and percentage for each level.

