5.7 Safety evaluation

- **Occurrence of adverse event**

- For adverse event (AE), adverse drug reaction (ADR), unexpected adverse event (UAE) and serious adverse event (SAE), the total number of subjects, the number of events, the occurrence rate and 95% confidence interval will be summarized.
- AE and ADR will be classified by the system-organ class (SOC) and preferred term (PT) using WHOART (WHO Adverse Reactions Terminology) for nth investigation report and MedDRA (Medical Dictionary for Regulatory Activities) for re-examination report, and summarized by the number of subjects, the occurrence rate and the number of events.
- The details of unexpected adverse event, serious adverse event and adverse event of subjects who are excluded from safety evaluation in accordance with paragraph 5.1.1 will be listed.
- Severity, causal relationship, actions taken regarding Pergoveris™ administration and progress of AE categorized by SOC and PT using WHOART for nth investigation report and MedDRA for re-examination report will be analyzed by presenting the number of events and

percentage. If there are several levels for severity, causal relationship, actions taken regarding Pergoveris™ administration and progress of the same AEs, the level that will be used for the analysis will be the worst one on subject level.

▪ **Factors that might affect the safety evaluation**

The occurrence of adverse event for each factor of demographics (age), baseline characteristics (concurrent disease, period for infertility, allergic history, previous assisted reproductive technology experience, luteinizing hormone, follicle stimulating hormone, previous treatments for infertility, concomitant medication), Pergoveris™ exposure (average daily dose, total duration, total dose) and special population (hepatic impairment, renal impairment) will be presented by the frequency and rate with 95% confidence interval. The AE rate for each factor will be analyzed using Pearson's chi-square test or Fisher's exact test.

Additionally, the occurrence of adverse event for all factors described above will be analyzed using multivariable logistic regression.

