5.8 Efficacy evaluation

▪ **Follicular growth and clinical pregnancy**

- Follicular growth: The frequency and percentage of subjects who are thought to be 'effective' (at least one follicle in more than 17mm of mean diameter on ultrasonography) will be presented.
- Clinical pregnancy: For the subjects who underwent clinical pregnancy test (urine HCG test or ultrasonography), the frequency and percentage of subjects who are pregnant (urine HCG test 'Positive' or ultrasonography 'Yes') will be presented.

▪ **Factors that might affect the effectiveness in follicular growth**

The effectiveness in follicular growth for each factor of demographics (age) and baseline characteristics (concurrent disease, period for infertility, allergic history, previous assisted reproductive technology experience, luteinizing hormone, follicle stimulating hormone, previous treatments for infertility, concomitant medication), Pergoveris™ exposure (average daily dose, total duration, total dose) and special population (hepatic impairment, renal impairment) will be presented by the frequency and percentage. The effective rate for each factor will be analyzed using Pearson's chi-square test or Fisher's exact test.

Additionally, the effectiveness for all factors described above will be analyzed using multivariable

logistic regression.

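### Sections 5.7 and 5.8 adjust pre-treatment factors for whole-course dose and duration in one regression, so their adjusted estimates may be biased in either direction as measures of overall influence

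*SAP*

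**What the plan says.** Section 1 sets the aim of analysing safety and efficacy "as well as factors likely to influence safety and efficacy". It does not say whether overall influence is meant, or influence at a given dose and course length.

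Sections 5.7 and 5.8 use the same list of factors:

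- age;
- concurrent disease, period for infertility, allergic history, previous ART experience, and "luteinizing hormone, follicle stimulating hormone, previous treatments for infertility, concomitant medication";
- "Pergoveris™ exposure (average daily dose, total duration, total dose");
- hepatic and renal impairment.

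Each factor is first tested alone by chi-square or Fisher's exact test. A single regression per outcome follows. For adverse events: "Additionally, the occurrence of adverse event for all factors described above will be analyzed using multivariable logistic regression". For follicular growth: "Additionally, the effectiveness for all factors described above will be analyzed using multivariable" logistic regression.

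Section 5.5 makes the exposure variables whole-course quantities: "Administration period is defined as the sum of each administration period", and "Total dose is defined as the sum of total doses on each administration period". Average daily dose is the ratio of the two. Nothing is cut off at the onset of the adverse event or at the follicle assessment. No adjusted model without exposure is planned.

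**The concern.** Age, LH, FSH and infertility history are fixed before the first injection. Dose and duration accumulate afterwards and may depend on them. A coefficient for age with dose and duration held fixed answers a narrower question than whether age influences the outcome, and the SAP neither states nor justifies that narrower question.

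Two mechanisms are involved. If a baseline factor acts partly by changing the amount or length of treatment, adjusting for exposure removes that part. If duration also reflects an unmeasured trait such as ovarian responsiveness, adjusting for it creates an association between the baseline factor and that trait, and so a selection bias.

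At stake are the only adjusted estimates for the baseline factors. A real determinant may look weak, or a factor with no influence may look like a determinant. Because the sign of the error is unknown, a reader cannot allow for it.

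**Working it through.** **Inputs from the SAP.** The factor list and single model (5.7, 5.8), whole-course exposure (5.5), the median split (5.5) and a minimum of 600 cases (section 3). The SAP states no effect size, power or rule for setting dose or course length, so there is no planned figure to reproduce. All effect sizes below are assumptions.

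**Check 1: direction of the shift.** A binary baseline factor X is present in half the women.

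- log(daily dose) = constant + 0.125·a·X + noise (SD 0.15)
- log(duration) = constant + 0.25·a·X + 0.25·k·U + noise (SD 0.25), with U an unmeasured standard normal trait
- total dose = daily dose × duration; z = standardised log(total dose)
- logit P(outcome) = constant + c·X + b·z − k·U

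With a = 1, X raises the typical daily dose by exp(0.125) = 1.13 and duration by exp(0.25) = 1.28. The constant in the outcome model is −2.2 in the first four rows and 1.0 in the rest. There were 400,000 subjects per scenario. Odds ratios (OR) for X:

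| Scenario | a, b, c, k | No exposure | Three median-split terms | Continuous log dose and log duration |
|---|---|---|---|---|
| Effect wholly through exposure | 1, 0.8, 0, 0 | 2.32 | 1.29 | 1.02 |
| Partly through exposure | 1, 0.6, 0.4, 0 | 2.72 | 1.73 | 1.46 |
| X does not change exposure | 0, 0.6, 0.5, 0 | 1.63 | 1.66 | 1.67 |
| Exposure does not change outcome | 1, 0, 0.5, 0 | 1.64 | 1.65 | 1.65 |
| Opposing paths | 1, 0.6, −0.8, 0 | 0.88 | 0.54 | 0.46 |
| Opposing paths, near offset | 1, 0.8, −0.9, 0 | 0.98 | 0.52 | 0.41 |
| Duration reflects unmeasured response, X has no effect | 1, 0, 0, 0.8 | 0.99 | 1.29 | 1.41 |
| Same, X lowers response | 1, 0, −0.5, 0.8 | 0.64 | 0.82 | 0.90 |

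A repeat with 1,000,000 subjects gave the same pattern, with ORs within about 0.05. The shift can go towards 1, away from 1, or be almost nil, and an effect can appear where none exists.

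**Check 2: a case closer to this setting.** Half the women are older. Days to the first follicle above 17 mm are N(10, 3) in younger women and N(10 + d, 3) in older women. Treatment ends at response or at a stop day N(14, 2). The unadjusted OR has a closed form. The SD of the difference is √(3² + 2²) = √13 = 3.61, so for d = 2:

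- younger: P(response) = Φ(4/3.61) = 0.866, odds 6.48
- older: P(response) = Φ(2/3.61) = 0.710, odds 2.45
- OR = 2.45/6.48 = 0.38

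Simulated age ORs for response:

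| Delay d | No duration | Median-split duration | Continuous duration |
|---|---|---|---|
| 1 day | 0.60 | 0.73 | 0.79 |
| 2 days | 0.38 | 0.53 | 0.61 |
| 3 days | 0.24 | 0.37 | 0.45 |

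If the adverse event risk is 1% per treated day and d = 2, the age OR for adverse events goes from about 1.17 to 1.06 (median split) and 1.00 (continuous).

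**Check 3: visibility at 600 women.** Under the Check 2 assumptions, the chance that age reaches p < 0.05 for response falls from about 60% to about 25% (d = 1) and from about 99% to about 80% (d = 2) when median-split duration is added. For adverse events (d = 2) it falls only from about 10% to about 6%. The standard error of the log OR is about 0.28, so the 95% interval spans a factor of exp(1.96 × 0.28) = 1.73 either way.

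**The case against.** A reader might infer that these regressions necessarily understate or remove the influence of baseline factors. The SAP does not support that. It would require the factor to change dose or duration, and exposure to move the outcome in the same direction as the factor. The SAP says nothing about either link, and Check 1 shows the other outcomes.

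Four further objections carry weight.

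- **Check 2 is not pure mediation.** Treatment there ends at response, so duration is partly a consequence of the outcome. Its efficacy shifts mix mediation with that reverse dependence and cannot size mediation alone. This stands.
- **The safety example is small.** Safety is the primary objective, and at 600 women the adverse event effect in Check 2 would rarely be detected under either model. This stands for that example.
- **One-factor results remain.** The planned tables and tests by single factor do not condition on exposure, so a crude association of age or LH with outcome would still be visible. This stands, but those tests do not adjust for other baseline factors, such as period for infertility when age is examined.
- **The joint model is legitimate.** Dose and duration are listed factors, their own coefficients need baseline adjustment, and section 1 does not say which kind of influence is meant. This supports keeping the joint model, but not making it the only adjusted analysis.

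The SAP does not name odds ratios as output; that is inferred from logistic regression. The annexed dummy tables are not shown.

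**Conclusion.** The concern holds as a matter of structure. The only adjusted estimates for pre-treatment factors are conditioned on exposure that arises after them, so they do not measure overall influence and may be biased in either direction. In Check 1 the OR was attenuated (2.32 to 1.29), inflated (0.88 to 0.54), spurious (0.99 to 1.29) or nearly unchanged (1.63 to 1.66; 1.64 to 1.65). These figures show what is possible under assumed effects and do not predict this study's results.

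The importance is moderate. The regression supplements descriptive rates and one-factor tests, but the search for influential factors is part of the stated objective and the correction is cheap.

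**What to change.** In each of sections 5.7 and 5.8:

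1. Specify a logistic model with pre-treatment factors only: age, concurrent disease, hepatic and renal impairment, period for infertility, allergic history, previous ART experience, LH, FSH and previous treatments for infertility. Because section 5.6 derives hepatic and renal impairment from the concurrent disease record, state how the overlap is coded.
2. Include concomitant medication only if it was started before Pergoveris. Section 4.6 already collects start dates.
3. Report the adjusted baseline-factor estimates from this model.
4. Show the model that adds the exposure variables as a second, separately labelled analysis, and state that its baseline coefficients refer to women with the same dose and course length.

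The cost is a change of SAP wording, one extra model and one extra set of estimates per outcome. No new data are needed and no clinical rule is affected.

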5.8 Efficacy evaluation

▪ **Follicular growth and clinical pregnancy**

- Follicular growth: The frequency and percentage of subjects who are thought to be 'effective' (at least one follicle in more than 17mm of mean diameter on ultrasonography) will be presented.
- Clinical pregnancy: For the subjects who underwent clinical pregnancy test (urine HCG test or ultrasonography), the frequency and percentage of subjects who are pregnant (urine HCG test 'Positive' or ultrasonography 'Yes') will be presented.

▪ **Factors that might affect the effectiveness in follicular growth**

The effectiveness in follicular growth for each factor of demographics (age) and baseline characteristics (concurrent disease, period for infertility, allergic history, previous assisted reproductive technology experience, luteinizing hormone, follicle stimulating hormone, previous treatments for infertility, concomitant medication), Pergoveris™ exposure (average daily dose, total duration, total dose) and special population (hepatic impairment, renal impairment) will be presented by the frequency and percentage. The effective rate for each factor will be analyzed using Pearson's chi-square test or Fisher's exact test.

Additionally, the effectiveness for all factors described above will be analyzed using multivariable

logistic regression.

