4.8 Efficacy items

- 1) HCG administration
- 2) Follicular growth
- 3) Clinical pregnancy
- 4) Urine HCG test
- 5) Ultrasonography

5. Statistical methodology

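### The clinical pregnancy rate in SAP section 5.8 pools scan-positive subjects with subjects positive on urine hCG alone, and the text asks for no split by test

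*SAP*

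**What the plan says.** Section 5.8 (Efficacy evaluation) sets the denominator with "For the subjects who underwent clinical pregnancy test (urine HCG test or ultrasonography"), so either test is enough to enter it. It sets the numerator with "the frequency and percentage of subjects who are pregnant (urine HCG test 'Positive' or ultrasonography 'Yes') will be presented". The text of 5.8 asks for no other pregnancy result.

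Section 4.8 (Efficacy items) lists three separate entries: "3) Clinical pregnancy", "4) Urine HCG test" and "5) Ultrasonography". The visible text does not rank one test above the other and asks for no count of subjects in whom the two disagree. Section 5.3 (Handling of missing data) fills in only partial drug administration dates, so an absent scan stays absent and a urine-positive subject without one is still counted.

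The only relevant count in the SAP is in section 3: "A total of 600 cases or more shall be reported as per the number of report cases". It is a regulatory number of cases, not a number tested for pregnancy.

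**The concern.** Once the urine test is positive, the scan has no effect on the result. A recorded negative scan and a scan never done both leave the subject in the numerator, beside subjects whose scan was positive. The rule does settle disagreement between the tests, but always in favour of pregnant, and it does not show how often that happened.

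A reader of the report would see one percentage under the label of clinical pregnancy and could not tell how much of it rests on ultrasound. Clinical pregnancy is one of the two efficacy results described in 5.8, so the figure is likely to be quoted. What is at stake is its interpretation. No hypothesis test, model or sample size depends on it.

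**Working it through.** The SAP states no pregnancy rate, testing rate or precision, so there is no planned figure to reproduce. The check has three parts: what the rule does, how large the effect can be, and why the denominator matters.

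**1. The rule, case by case.** Cross urine hCG (positive, negative, not done) with ultrasonography (yes, no, not done) and apply 5.8:

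| Urine hCG | Scan | In denominator | Counted pregnant | Scan positive |
|---|---|---|---|---|
| Positive | Yes | yes | yes | yes |
| Positive | No | yes | **yes** | **no** |
| Positive | Not done | yes | **yes** | **no** |
| Negative | Yes | yes | yes | yes |
| Negative | No | yes | no | no |
| Negative | Not done | yes | no | no |
| Not done | Yes | yes | yes | yes |
| Not done | No | yes | no | no |
| Not done | Not done | no | no | no |

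Eight of the nine combinations enter the denominator and five count as pregnant. Two of those five have no positive scan.

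**2. Size.** Let T be the number tested, a the number with a positive scan, d the urine-positives with a negative scan, and b the urine-positives with no scan.

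- Rate under 5.8: (a + d + b)/T
- Scan-positive rate over the same subjects: a/T
- Excess: (d + b)/T, which is never negative

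Neither d + b nor T is in the SAP. The values below are assumptions; T = 600 takes the section 3 minimum and supposes that every case was tested.

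| d + b | T = 600 | T = 400 | T = 200 |
|---|---|---|---|
| 0 | 0 | 0 | 0 |
| 1 | 0.17 points | 0.25 points | 0.5 points |
| 6 | 1.0 | 1.5 | 3.0 |
| 30 | 5.0 | 7.5 | 15.0 |

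For example, 30/400 = 7.5 points.

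The size can also be scaled by the urine-positive rate. Suppose that 20% to 40% of tested subjects are urine-positive, that 70% to 100% of these have a positive scan, and that nobody else does (all assumed). The excess then runs from 0 (every urine-positive has a positive scan) to 0.40 × (1 − 0.70) = 12 points.

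**3. Why both denominators are needed.** Take T = 400, a = 100, d = 15 and b = 10, all assumed.

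- Rate under 5.8: (100 + 15 + 10)/400 = 125/400 = 31.25%
- Scan-positive over all tested: 100/400 = 25.0%
- Difference: 25/400 = 6.25 points

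The scan-positive rate over scanned subjects also depends on u, the number of urine-negatives not scanned. The number scanned is S = T − b − u:

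- u = 0: 100/390 = 25.6%
- u = 50: 100/340 = 29.4%
- u = 150: 100/240 = 41.7%

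This rate exceeds 31.25% once S falls below 400 × 100/125 = 320. The statement that the 5.8 rate is at least the scan-positive rate therefore holds over all tested subjects, not over scanned subjects. A scan-positive percentage without its denominator would be ambiguous too.

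**The case against.** The strongest case against is that nothing in the SAP is wrong by its own terms. Section 5.8 states numerator and denominator openly, they fit each other, and it treats both examinations as pregnancy tests. A reader might infer that the SAP contradicts itself, or that a urine-positive subject is miscounted. The document does not support either reading: it nowhere says that clinical pregnancy requires a scan. Nor can it be faulted for lacking test timing or a confirmatory-scan rule, since the protocol, which is not at hand, may give them. This part of the objection stands and limits the point to how the result is reported.

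Second, section 5.2 promises counts and percentages by category for categorical variables, and the two tests are listed items, so separate counts by test may be produced anyway. The dummy-table annex is not shown and may contain them. That is fair, and those rows cannot be called missing. However, 5.8 does not name them, separate totals would not show how many subjects were discordant, and extra rows would leave unchanged the numerator that 5.8 attaches to the label.

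Third, section 4.8 gives item names without response options. It is likely, but not stated, that a negative scan is recorded separately from a scan not done. The fix has to allow for that.

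Fourth, a reader might wish to bracket the true rate, for instance by adding unscanned urine-positives to the scan-positives and calling the sum an upper limit. The SAP does not support this. It would require that unscanned urine-negatives are not pregnant and that every negative scan is final, and neither can be checked from the document. Likewise, the listing of hCG administration in 4.8 is no evidence of false urine positives, because the SAP draws no link between the two.

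**Conclusion.** The point holds as a minor one about interpretability. The *or* rule in 5.8 merges scan-positive subjects with urine-only positives in a single percentage, which over all tested subjects is at least the scan-positive rate and exceeds it by (d + b)/T. That relation follows from the wording alone and needs no assumption about rates.

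The size does not follow from the SAP. It is zero if every urine-positive subject has a positive scan, and every non-zero figure given here rests on assumed counts. A claim that the reported rate will be materially inflated would go further than the document allows. The primary objective is safety, and both the efficacy dataset and the factor analyses rest on follicular growth, so no inference changes.

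**What to change.** In section 5.8, use the urine hCG and ultrasonography items already listed in 4.8 to report:

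- (a) subjects with a positive scan as their own line, with number and percentage over all tested subjects and over scanned subjects, printing both denominators;
- (b) the number of urine-positive subjects with a negative scan and the number with no scan recorded, on separate lines as far as the recorded data distinguish them;
- (c) the present either-test rate, kept but relabelled as positive pregnancy test (urine hCG or ultrasonography).

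Attach no upper limit or ceiling to these lines. Tying the clinical pregnancy label to line (a) is a proposal for clarity, not the correction of a breach, and should be checked against any definition in the protocol.

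The cost is a change of wording and a few table rows, some of which the annex may already hold. No new data item is proposed, and no test or sample size changes. The one drawback for the sponsor is that the rate labelled clinical pregnancy, over all tested subjects, may come out lower.
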